6. PROCEDURES

6.1. Screening Evaluations

This study will be conducted at approximately 5 sites in the US. Additional sites may be added.

Each patient who enters into the screening period for the study receives a unique patient identification number before any study-related procedures are performed. The patient identification number will be assigned. This number will be used to identify the patient throughout the clinical study and must be used on all study documentation related to that patient.

The patient identification number must remain constant throughout the entire clinical study; it must not be changed after initial assignment, including if a patient is rescreened.

Before patients may be entered into the study, the Sponsor requires a copy of the site's written IRB/IEC approval of the protocol, informed consent form, and all other patient information and/or recruitment material, if applicable. A signed and dated Institutional Review Board (IRB) approved informed consent form (latest approved version) must be obtained from each patient prior to performing any study-specific procedures. All patients or legally acceptable representatives must personally sign and date the consent form before commencement of study-specific procedures. Patients who lack capacity to understand protocol requirements will be excluded. Adverse Events are to be collected for a patient upon signing the informed consent until 28 days after last dose of study drug.

Screening evaluations will be performed for all patients to determine study eligibility. These evaluations must be completed within 28 days prior to enrollment. Any questions regarding patient eligibility should be directed to Aadi or other sponsor-nominated representatives or designees for approval.

The following procedures are to be completed during the **screening period**, after signed informed consent has been obtained, designated in the Schedule of Assessments, [Table 2](#). The 6MWD test will be conducted following guidelines by American Thoracic Society [\[52\]](#).

- Informed consent
- Medical history, demographics
- Complete blood count with differential and chemistry panel
- Physical exams, vital signs, height, and weight
- Serum pregnancy test
- NT Pro-BNP
- CRP
- Troponin

- Biomarker test (optional)
- Fasting lipid test
- SF-36 and emPHasis10 questionnaire
- Echocardiogram
- 6MWD test
- WHO Functional Class
- Pulmonary function test
- Right heart catheterization
- Concomitant medication
- HIV test
- Hepatitis B surface antigen, hepatitis B and C antibody tests
- Adverse Events

A patient is considered eligible when the investigator decides that the patient has met all eligibility criteria. The investigator is to document this decision and date, in the patient's medical record and in/on the electronic case report form (eCRF).

All screening tests and procedures must be performed within 28 days of study day 1. Once eligibility is confirmed, a site representative will complete and fax a patient eligibility criteria worksheet to an Aadi representative. The Aadi representative will acknowledge receipt of the paperwork and confirm enrollment for that individual patient.

6.2. Dose-finding Safety Part (up to 16 weeks)

A patient is considered enrolled on study day 1 when the IP, ABI-009, is first administered. ABI-009 is to be administered after all other protocol-specified pre-dose assessments have been performed during each visit that it is required. ABI-009 will be administered weekly for 16 weeks. All weekly visits are allowed to occur in a window of ± 3 days.

6.2.1. Every Week Assessments During the 16-week Dose-finding Safety Part

The following assessments will be performed every week:

- Physical exams, vital signs and weight
- Complete blood count with differential and chemistry panel
- Sirolimus PK
- Concomitant medications
- Adverse Events

Week 1 evaluations may be omitted if screening evaluations are performed within 72 hours. For complete analyte listing, refer to [Table 3](#).

Table 3: Analyte Listing

Chemistry	Hematology	Other Labs
Sodium	WBC	Pregnancy test
Potassium	RBC	Sirolimus PK
Bicarbonate	Hemoglobin	HIV
Chloride	Hematocrit	HBV sAg
Total protein	MCV	HBV cAb
Albumin	MCH	HCV Ab
Calcium	MCHC	Total Cholesterol
Magnesium	RDW	HDL
Phosphorus	Platelets	LDL
Glucose	Differential:	Triglyceride
BUN	-Neutrophils	Biomarker development
Creatinine	-Lymphocytes	NT Pro-BNP
Total bilirubin	-Monocytes	CRP
Alkaline phosphatase	-Eosinophils	Troponin
AST (SGOT)	-Basophils	
ALT (SGPT)		
Amylase		
Lipase		

6.2.2. Every 4-Week Assessments During the 16-week Dose-finding Safety Part

The following assessments will be performed every 4 weeks at week 5, week 9, and week 13:

- NT Pro-BNP
- CRP
- Troponin
- Fasting lipids
- Echocardiogram
- 6MWD test
- WHO Functional Class
- Pulmonary function test

All efficacy measurements will occur prior to the administration of ABI-009 during the visit.

6.2.3. Efficacy Assessment During the 16-week Dose-finding Safety Part

Efficacy assessment will occur at baseline and at EOT Visit (to evaluate the utility (potential for clinical efficacy) of ABI-009 in the treatment of PAH as measured by a change in PVR and other hemodynamic parameters. Change from baseline in 6MWD (absolute difference in distance), echo cardiographic assessments and WHO functional class will be measured. Changes from baseline to week 17 in 36-Item Short Form Health Survey (SF-36) physical functioning scale and in emPHasis10 questionnaire will be measured as exploratory endpoints.

For efficacy assessment, all sites need to refer to standard instructions provided, including Right Heart Catheterization (RHC), RHC Parameter Worksheet, Six Minute Walking Test (6MWT) Instruction, Borg dyspnea index (BDI), WHO Classification Worksheet, Echocardiogram Instruction, and Pulmonary Function Test Instruction. Echocardiogram and RHC assessments will be submitted to centralized core labs for analysis.

6.3. End of Treatment Visit Assessment

End of Treatment Visit assessment for a patient is when efficacy and safety assessments and procedures are performed after the last treatment in the 16-week Dose-finding Safety Part. For patients who complete the 16-week treatment, EOT assessments occur on week 17 (± 3 days) and for patients who do not complete the 16-week treatment, EOT assessments must occur within 4 weeks (± 7 days) after the last dose of ABI-009.

- Physical exams, vital signs, and weight
- Complete blood count with differential and chemistry panel
- Concomitant medications
- Adverse Events
- Urine pregnancy
- NT Pro-BNP
- CRP
- Troponin
- Biomarker analysis (optional)
- Fasting lipids
- Echocardiogram
- 6MWD test
- WHO Functional Class
- Pulmonary function test
- Right heart catheterization

- SF-36 and emPHasis10 questionnaire

For patients who fail to complete the 16-week treatment, RHC can be performed if patients opt to have the procedure. RHC results from these patients will be analyzed separately from those of patients who complete the 16-week treatment.

6.4. Pharmacokinetic Study

A PK study of sirolimus will be performed with limited PK sampling on all patients in the dose-finding portion of the study during the first 4 weeks of treatment, assessed via central lab:

- Blood samples will be obtained on day 1 (week 1) and will be taken immediately predose (before infusion), immediately after termination of infusion (end infusion), then at 1 hr, 2 hrs, and 4 hrs post infusion. Thereafter, blood samples will be taken every week immediately predose for the next 3 weeks (weeks 2, 3, and 4) to determine a trough level.

Additional PK samples for sirolimus analysis will be obtained for local lab assessment to help correlate AEs with blood levels during treatment:

- From all treated patient in the 16-week Dose finding Safety Part (including expansion cohort/s): Immediately predose starting at week 2 and continuing for the duration of the study
- From all treated patients in the up to 32 weeks of Extension Part: Immediately predose starting at week E2 and continuing every other week for the duration of the study
- Optional PK samples for consenting patients: During weeks 1 and 3 of the Dose-finding Safety Part at 24, 48, and 72 hours post infusion.

Note that T = 0 is defined as the start of infusion, ie, all sample collection times are relative to the start of infusion. The sample at the end of the infusion is collected immediately after the infusion is stopped. If the duration of infusion is changed, the sample should be collected immediately before termination of the infusion and the time noted.

Whole-blood samples will be collected in EDTA tubes for determination of sirolimus in a central laboratory.

Sample Handling for Central Lab:

- Collect approximately 4 mL blood into vacutainer tubes containing EDTA as the anticoagulant.
- Mix the whole blood gently but thoroughly in the tube immediately after collection.
- Split the sample into two tubes. One tube will be kept as a back-up sample.
- Ensure that both tubes are labeled identically.
- Store the blood samples deep frozen at a temperature between -20 and -80°C.
- The samples will be shipped to a designated laboratory.

Sample Labeling:

The following information should be on each sample:

- Protocol number
- Patient ID
- Nominal sample time point
- Collection clock time and date

A simple regression model will be applied to assess the relationship of the pharmacokinetic parameters with dose.

6.5. Samples for Optional Biomarker Analysis During the 16-week Dose-finding Safety Part

For consented patients enrolled in the expansion cohort, blood samples will be collected for blood outgrowth endothelial cell (BOECs) at baseline and EOT to correlate response to therapeutic intervention with ABI-009.

6.6. Assessments During the Optional Extension Part

For patients who tolerated ABI-009 well and showed clinical benefit during the Dose-finding Safety Part, based on the investigator and Safety Committee's judgement can continue treatment for up to an additional 32 weeks. All assessments must be done prior to dosing:

Every visit when ABI-009 is given (E1 through E32):

- Physical exams
- Vital signs and weight
- Concomitant medications

Every 2 visits when ABI-009 is given from E2 through E32:

- Complete blood count with differential and chemistry panel

Sirolimus Every 4 weeks when ABI-009 is given (E5 through E29):

- Lipids

Every 8 weeks (ie, at weeks E9, E17, E25, and E33):

- 6MWD test
- WHO Functional Class
- Pulmonary function test
- NT Pro-BNP

Every 16 weeks (ie, at weeks E17 and E33):

- SF-36 and emPHasis10 questionnaire

7. DESCRIPTION OF STUDY TREATMENTS

7.1. ABI-009 Dosage, Administration, and Schedule

The planned treatment period is 16 weeks, with ABI-009 given weekly. Patients, who based on the investigator and Safety Committee's assessment, tolerate ABI-009 and show clinical benefit during the 16-week Dose-finding Safety Part, and for whom there are no alternative therapies available, may opt to continue therapy in the optional Extension Part, with ABI-009 given weekly at the originally assigned dose (or lower, if permanently reduced) for up to 32 additional weeks. A physician must be available at the time of administration of IP on dosing days that correspond to study visits. Supportive care per the institution's normal standard of care including concomitant medications can be provided at the investigator's discretion.

In the dose-finding portion of the study, 4 dose levels of ABI-009 will be tested in cohorts of 3 patients each (1, 2.5, 5, and 7.5 mg/m², see [Table 1](#) and below), using the 3+3 dose escalation de-escalation design. There will be no intra-patient dose escalation allowed. Escalation to the next dose level with a new cohort of 3 patients will occur after no DLT was observed in the first treatment cycle of 4 weeks. If a DLT occurs in a cohort, additional 3 patients will be recruited to the cohort. If no further DLTs occur, then a new cohort of 3 patients at the next higher dose level can be enrolled. If 2/6 patients at dose level 1a experience a DLT, then that cohort will be closed to further enrollment and the study may be terminated. If 2/6 patients at dose levels 2a, 3a, or 4a experience a DLT, then the previous dose level is considered the MTD.

It is estimated that a maximum of up to 24 patients will be required to achieve the MTD; however, MTD could be reached with as few as 9 patients. Patients will be allowed to dose reduce by one dose level for reasons of toxicity, with a maximum of 2 dose reductions allowed for a patient. At the lowest dose level, a dose reduction of 25% will be allowed.

Dose Level	1a	2a	3a	4a
ABI-009 Weekly Dose (mg/m ²)	1	2.5	5	7.5

Note: The original protocol included dose levels 1 (10 mg/m²), 2, (20 mg/m²) and 3 (30 mg/m²), and dose level -1 (5 mg/m²).

7.2. Dose Modification and Stopping Rules

7.2.1. Dosage Adjustments, Delays, Rules for Withholding or Restarting, Permanent Discontinuation

If treatment cannot be administered on the planned visit date, ABI-009 may be administered \pm 3 days from the scheduled date. Prior to ABI-009 administration, patients must meet the following hematological requirements:

- ANC \geq 1.5 x 10⁹/L
- Platelet count \geq 100 x 10⁹/L

- Hemoglobin ≥ 9 g/dL

The treatment will be on hold up to 14 days until the patient has fulfilled these criteria.

In the event of clinically significant AE in any part of the study, treatment may be withheld, and supportive therapy administered as clinically indicated. If the toxicity or event is not grade 3/4 and resolves to baseline or grade 1 in less than or equal to 14 days of stopping therapy, then treatment may be restarted.

A DLT is defined as a study-drug -related grade ≥ 3 hematologic AE or persistent intolerable nonhematologic AE of any grade that requires dose reduction or permanent discontinuation of the study-drug, in the opinion of the investigator.

Dose reduction of ABI-009 to the next lower dose level should be considered as clinically indicated for patients who are receiving ABI-009 at above the lowest dose level. At the lowest dose level, a dose reduction of 25% will be allowed. Once a dose has been reduced, it must not be increased to the previous level. A maximum of 2 dose reductions are allowed for a patient in the entire duration of the study.

The maximum delay between a missed scheduled dose and the next one (whichever dose was missed) should not be longer than 14 days. Approval from the Medical Monitor is required to restart study treatment after ≥ 21 days of interruption.

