1.2.3.6. Clinical Studies with ABI-009

In a phase 1 dose escalation, tolerability and pharmacokinetics study conducted at MD Anderson Cancer Center (Protocol CA-401), ABI-009 was well tolerated with evidence of responses and SD in various solid tumors including renal cell carcinoma and bladder cancer, both of which typically express mTOR [12]. Twenty-six patients were treated with 45, 56.25, 100, 125, 150 mg/m² ABI-009 per week for 3 weeks, followed by a week of rest (28-day cycle). ABI-009 administered intravenously. The maximum tolerated dose (MTD) was established at 100 mg/m².

Nineteen patients were evaluable for efficacy. One patient in the 45 mg/m² (95 mg actual sirolimus dose) cohort diagnosed with adenocarcinoma of the kidney and with bone and intrathoracic metastases had a confirmed PR. The target lesion of this patient was reduced by 35.1% and the duration of response lasted 183 days. Two (11%) patients (at doses 45 and 125 mg/m², with actual sirolimus doses of 88 mg and 193 mg, respectively) had an overall tumor evaluation of SD (confirmed): 1 patient with mesothelioma had SD for 365 days and 1 patient with a neuroendocrine tumor in the left axillary node had SD for 238 days.

In the phase 1 study described above, for all cohorts and all grades, 25 of 26 (96%) patients experienced at least 1 AE. The most common AEs were mucosal inflammation (10 patients, 38%), fatigue (7 patients, 27%), rash (6 patients, 23%), diarrhea (6 patients, 23%), and nausea (5 patients, 19%). Most of these AEs were grade 1/2 events, with only 3 grade 3 nonhematologic AEs (2 elevated AST and 1 dyspnea). Specifically, at the maximum-tolerated dose (MTD, 100 mg/m²), all 7 patients experienced at least 1 AE of any grades, and the most common AEs were mucositis and fatigue (5 patients, 71% each). Four (15%) patients experienced at least 1 treatment-related SAE, including arrhythmia (grade 2) and mood alteration (grade 3) both in the 125 mg/m² cohort, vomiting (grade 3) in the 45 mg/m² cohort, and dyspnea (grade 3) in the 100 mg/m² cohort.

The most common hematologic AEs, for all cohorts and grades, were thrombocytopenia (58%), followed by hypokalemia (23%), anemia and hypophosphatemia (19% each), and neutropenia and hypertriglyceridemia (15% each). Most of these events were grade 1/2, and only 1 grade 4 hematologic event occurred (thrombocytopenia in the 150 mg/m² arm). At the MTD, the only hematologic AE was a grade 3 anemia.

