10. STATISTICAL CONSIDERATIONS

10.1. Study Endpoints

Primary Endpoints:

MTD, DLTs, and toxicities and safety profile of 16 weeks, as well as safety profile of the up to 48 weeks of ABI-009 given IV, in patients with PAH who are WHO Functional Class II or III despite best available background therapy.

In the dose-finding portion of the study, 4 dose levels of ABI-009 will be tested in cohorts of 3 patients each (1, 2.5, 5, and 7.5 mg/m²), using the 3+3 dose escalation design. There will be no intra-patient dose escalation allowed. Escalation to the next dose level with a new cohort of 3 patients will occur after no DLT was observed in the first treatment cycle of 4 weeks. If a DLT occurs in a cohort, additional 3 patients will be recruited to the cohort. If no further DLTs occur, then a new cohort of 3 patients at the next higher dose level can be enrolled. If 2/6 patients at dose level 1a experience a DLT, then that cohort will be closed to further enrollment and the study may be terminated. If 2/6 patients at dose levels 2a or 3a experience a DLT, then the previous dose level is considered the MTD.

The treated population will be the analysis population for all safety analyses. Adverse events will be coded using the Medical Dictionary for Medical Activities (MedDRA) and grouped by their system organ class and preferred term. Summary tables will include the number and percentage of treatment-emergent and treatment-related AEs, AEs of special interest, SAEs, and incidence of patients experiencing dose modifications, dose delay/dose not given, dose interruptions, and/or premature discontinuation of IP due to an AE.

An external Safety Monitoring Committee (SMC) will assess safety data periodically as needed.

Secondary Endpoint(s):

The following will be measurements will be summarized at baseline and at 17 weeks (after 16 weeks of treatment in the Dose-finding Safety Part):

- pulmonary vascular resistance (PVR) by right heart catheterization
- pulmonary artery pressure (PAP)
- pulmonary capillary wedge pressure (PCWP)
- central venous pressure (CVP)

The following will be measurements will be summarized at baseline, 5, 9, 13, and 17 weeks:

- Doppler-echocardiographic assessments of right ventricular structure and function
- 6-minute walk distance (6MWD)
- WHO functional class
- Pulmonary function test

The following will be measurements will be summarized every 8 weeks of the Extension Part (ie, at week E9, E17, E25, and E33):

- 6MWD

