12. WITHDRAWAL FROM TREATMENT, PROCEDURES, AND STUDY

12.1. Discontinuation from Investigational Product

The following events are considered sufficient reasons for discontinuing a patient from the IP:

- AE(s) (that are intolerable)
- Physician decision
- Withdrawal of consent (from treatment only)
- Death
- Lost to follow up
- Protocol violation
- Other (to be specified on the eCRF)

The reason for treatment discontinuation should be recorded in the eCRF and in the source documents.

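### Section 7.2.1 sets no grade trigger for nonhematologic DLTs, so a resolved drug-related grade 3/4 event need not count and a cohort with several could still escalate

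*Combined protocol and SAP*

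**What the plan says.** The synopsis refers to section 7.2.1 for the DLT definition, and no other definition appears. A DLT is a drug-related grade 3 or higher "hematologic AE or persistent intolerable nonhematologic AE of any grade that requires dose reduction or permanent discontinuation" of study drug, as judged by the investigator. The nonhematologic arm accepts any grade, but the event must be persistent, must be intolerable, and must lead to reduction or permanent discontinuation. None of these terms is defined. Section 12.1 lists intolerable AEs among the reasons to stop drug, without further criteria.

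Under section 7.1, escalation "will occur after no DLT was observed in the first treatment cycle of 4 weeks". One DLT adds 3 patients to the cohort. Two DLTs in 6 patients at level 2a, 3a or 4a make the previous level the MTD. MTD and DLTs are primary endpoints (sections 2.2 and 10.1).

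Section 7.2.1 also has a restart rule. Drug may be withheld for a clinically significant AE. "If the toxicity or event is not grade 3/4 and resolves to baseline or grade 1 in less than or equal to 14 days", counted from when drug is held, dosing may resume. The rule does not mention grade 3/4 events that resolve. Separately, "Approval from the Medical Monitor is required to restart study treatment after" an interruption of 21 days or more.

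On oversight, section 10.1 says: "An external Safety Monitoring Committee (SMC) will assess safety data periodically as needed". It gives the committee no stated role in opening the next dose level. On sites, section 6.1 says: "This study will be conducted at approximately 5 sites in the US".

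**The concern.** A DLT rule should stop escalation when a dose proves toxic. Here severity alone triggers a DLT only for hematologic events. A severe nonhematologic reaction that is drug-related but subsides once drug is held can fall outside the definition, because an investigator may reasonably say that it did not persist. Several such reactions at one level could leave the DLT count at zero and open the next dose.

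Two things are at stake. The first is the safety of patients entering the next cohort. The second is the meaning of a primary endpoint: with an undefined word applied at about 5 sites and only 3 to 6 patients per level, scoring one event differently can change the escalation decision.

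**Working it through.** **1. The rule applied to a cohort.** Suppose all 3 patients at a level have a drug-related grade 3 or 4 nonhematologic AE in weeks 1 to 4, and each resolves after drug is held.
- Hematologic arm: not applicable.
- Nonhematologic arm: grade plays no part. If the investigator judges that a resolved event is not persistent, the event fails this arm.
- Score on that judgement: 0/3, so the level escalates.
- Score with a grade 3 or higher trigger: 3/3, so it does not.

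**2. The plan's own sample sizes.** Section 10.2 gives a maximum of 24 and a minimum of 9. Both reproduce: 4 levels × 6 = 24, and 3 at level 1a + 6 at level 2a = 9. The design is rule-based, so there is no alpha, power or effect size to check.

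**3. Escalation probability at one level.** A level passes with 0/3 DLTs, or with 1/3 followed by 0/3. If *p* is the chance that a patient has an event that counts,

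f(p) = (1 − p)^3 + 3p(1 − p)^5.

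Let *T* be the rate of drug-related grade 3 or higher nonhematologic AEs in the first 4 weeks, and *s* the share of these that resolve and are not counted. Then p = T(1 − s). Both are assumptions, and no other DLTs are assumed. For example, T = 20% and s = 0 give 0.8^3 + 3 × 0.2 × 0.8^5 = 0.512 + 0.197 = 0.709.

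| Assumed T | All count (s = 0) | Half count (s = 0.5) | None count (s = 1) |
|---|---|---|---|
| 5% | 0.973 | 0.993 | 1.000 |
| 10% | 0.906 | 0.973 | 1.000 |
| 20% | 0.709 | 0.906 | 1.000 |
| 1/3 | 0.428 | 0.780 | 1.000 |

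The last column is 1.000 by construction. The largest difference that the definition can make is 1.000 minus the first column: 0.027, 0.094, 0.291 and 0.572.

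With an independent 10% rate of other DLTs, p = 1 − 0.9(1 − T) if all events count. The pass probability is 0.906 if none of the resolved events count. If all count, it is 0.730 at T = 10% and 0.536 at T = 20%.

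**4. Can T be taken from the documents?** No. Section 1.2.3.6 describes 26 oncology patients. It reports 3 grade 3 nonhematologic AEs (2 AST elevations and 1 dyspnea), but its list of treatment-related SAEs names grade 3 mood alteration, vomiting and dyspnea. The lists share only dyspnea, and neither is limited to the first cycle. The lowest dose there was 45 mg/m², which is 45/7.5 = 6 times the top dose here, and the patients did not have PAH.

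**The case against.** **Investigator judgement.** A reader might infer that a resolved grade 3/4 nonhematologic event can never be a DLT. The text does not support that. With *persistent* undefined, an event that lasts until drug is held and then leads to dose reduction can be called persistent and intolerable. This stands: such an event need not count, but it may.

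**The restart rule.** Resumption is expressly allowed only for events below grade 3. On a restrictive reading, a held grade 3/4 event must lead to reduction or discontinuation, both of which are elements of the DLT definition. That narrows the gap but leaves persistence and intolerability open. Withholding is optional, the rule permits restart in one case without forbidding it in others, and it is not tied to the DLT definition. A reader might also infer that the two rules contradict each other. They do not: the restart rule is silent on these events.

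**Other safeguards.** SAEs are reported within 24 hours (section 11.3.2), and the sponsor can withdraw patients or stop the study (sections 12.3 and 13.5). Section 2.1 bases the MTD on the safety evaluation and lets the recommended phase 2 dose differ from it. The primary endpoint also includes the safety profile over 16 and up to 48 weeks. These make an unsafe escalation less likely, but none changes the count on which section 7.1 escalates.

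**A deliberate choice.** Counting intolerable events of any grade is broader at grades 1 and 2 and suits weekly add-on therapy. This is a fair reason to keep that arm, but not a reason to omit a trigger at grade 3.

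**Classification.** Section 1.2.3.6 lists electrolyte abnormalities among hematologic events, so a reader might infer that the two arms are blurred. That section is oncology background. Table 3 of this protocol places potassium and phosphorus under chemistry.

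**Conclusion.** The concern holds in this form: the definition lets a drug-related grade 3/4 nonhematologic AE that resolves go uncounted, so a cohort with several could be scored 0/3 and escalate. This rests on the wording of sections 7.2.1 and 7.1 and needs no assumed rate.

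The size of the effect cannot be estimated from the documents. With no other DLTs, the pass probability changes by less than 0.03 at an assumed rate of 5% or below, and by up to 0.29 at 20%. A reader might infer from the table that the trial is likely to pass a toxic dose or to set the MTD too high. The documents do not support that: the rates are assumed, the doses are far below the oncology range, and other oversight exists. The change is worth making because it is cheap and matters at the level that proves toxic.

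**What to change.** Keep the present definition and add one further limb: *or any study-drug-related grade ≥3 nonhematologic AE, except brief, correctable laboratory abnormalities listed by analyte and duration.* The list must be completed before use. Set the limb apart so that the investigator-opinion qualifier does not attach to it. Put no time limit in the definition itself, because the primary endpoint covers 16 weeks of treatment; keep the 4-week window for the escalation decision only.

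Apply the new definition prospectively to escalation and MTD decisions. Section 3.2 shows that the 7.5 mg/m² level was added later, so lower levels may already be cleared. For those levels:
- review the cycle-1 AE listings;
- report DLTs under both definitions;
- have the Safety Monitoring Committee review any level that would no longer clear, before further enrollment at or above it.

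The cost is an amendment, the exemption list and the listing review. Some cohorts may expand from 3 to 6, within the maximum of 24. The MTD may come out lower, and the change to a primary endpoint must be disclosed.
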